## **6 STATISTICAL CONSIDERATIONS**

### **6.1 Statistical Methods**

#### **6.1.1 General Analysis**

The initial analysis will involve describing the distribution of data. The primary exposure of interest is presence or absence of VUR. We will characterize exposed and unexposed subjects by all predictor variables. Categorical variables will be summarized by frequencies while continuous variables will be summarized by mean, median, standard deviation, and range. The purpose of this description is to identify any differences in the exposure groups that may explain differences in renal scarring or recurrent UTI, in addition to presence or absence of VUR. Analyses will need to be adjusted for any differences in these potentially confounding variables. We will also calculate correlations (Pearson or Spearman, depending on whether continuous or ordinal) and associations between the predictor variables. In those cases where there is a strong correlation or association, we will choose variables with more clinical relevance to be the candidate predictor variables for Aims 2 and 4.

#### **6.1.2 Analysis plans for Specific Aim 1 – Primary Outcome**

In order to test whether the proportion of children who have renal scarring on DMSA scan is equivalent among the CUTIE study patients who did not have VUR and the placebo-treated RIVUR study who did have VUR, we will calculate the difference in proportions and test whether the difference in proportions is less than 10% or not using a one-sided 0.05 significance level. We will therefore test the null hypothesis that the VUR group and non-VUR group are not equivalent and that the difference in the proportions of renal scarring between the groups is 10% or farther from zero in the same direction. If we reject this null hypothesis, the alternative hypothesis in this case is that the proportions of renal scarring in the two groups are equivalent, closer to each other than a 10% difference. This approach of essentially "reversing" the traditional roles of the null and alternative hypothesis is used to assure that the study is powered to detect equivalence, and not merely to conclude equivalence because differences were not significant on a traditional testing approach [which can occur simply because of a too small sample size]. As a secondary analysis, we will test using the same approach the proportion of children with severe scarring (grades 3 or 4 scarring on at least one kidney). The DMSA is planned to be done at 24 months after the index UTI, but if a DMSA is indicated and done sooner, and shows scarring, that DMSA will serve as the primary outcome.

If the subjects who agree to enroll in RIVUR differ from those who agree to enroll in CUTIE in ways that are associated with the development of renal scarring, then a comparison of renal scarring in these 2 groups will be confounded by these differences. Although a priori we do not anticipate such differences to emerge, in testing for differences in renal scarring we will adjust for potential risk factors for renal scarring (age, race, gender, fever) using multivariable logistic regression models. We will also determine whether the 2 groups are different in terms of other factors not known to be associated with renal scarring, and we will adjust for those factors as well in order to control for any potential unrecognized confounders. If any adjustment is found necessary to prevent bias, then we will also do hypothesis testing based on the 95% confidence interval of the odds-ratio calculated from the coefficient of the VUR variable in the logistic regression model, testing for equivalence as above.

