#### 1.1.2 Relationship of UTI and VUR to Renal Scarring

VUR is thought to increase the risk of UTI by increasing post-void residual and allowing less virulent strains of bacteria to ascend into the upper tract and infect the kidney. VUR is considered important in the evaluation and management of children with UTI because of the observed relationship between degree of VUR and subsequent renal scarring. In some studies, patients with high-grade VUR have been four to six times more likely to have scarring than those with low-grade VUR and eight to ten times as likely as those with no VUR. Based on these associations, a conceptual model has evolved postulating that the combination of recurrent UTI and VUR leads to renal scarring (Figure 2). As a result, management strategies have focused on surgical correction of VUR and/or prevention of UTI with prophylactic antibiotics.

Figure 2: Conceptual Model of Renal Scarring

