### 1.2.5 Evaluation of UTI

Finding	No. of Children (%)
Normal	185 (61.3)
Vesicoureteral reflux	
Grade I	25 (8.3)
Grade II	42 (13.9)
Grade III	45 (14.9)
Grade IV	5 (1.7)
Grade V	0

\* Cystourethrography was not performed in seven children.

[figure not shown]
Using data from their RCT of PO vs. IV antibiotics for UTI, **[name]** and colleagues challenged current thinking about the routine imaging of children following a first febrile UTI. In that clinical trial US and DMSA renal scans were performed to determine the presence of anatomic abnormalities and scintigraphic evidence of APN, respectively. Radiographic VCUG was performed 1 month later to determine the presence of VUR; a repeat renal scan was done 6 months later to determine the incidence

Version 4.23.2008

Table 5. N Engl J Med 2003; 348:195-202.

and extent of scarring. US results were normal in ~90% of children; of the abnormalities identified, none modified management of any patient. APN was diagnosed in 61% (187/306) of children based on initial DMSA scan. The extent of parenchymal involvement among patients with APN was 31%. Approximately 40% of children had VUR, most classified as Grades I to III (Table 5). Repeat scans were performed in 272/306 (88%) children, with renal scarring (mean ~8% of the renal parenchyma) noted in 26/272 (9.5%) children. Approximately 15% of children with APN at study entry had renal scarring 6 months later. VUR was the only clinical characteristic significantly associated with a higher likelihood of renal scarring (Figure 4). They concluded that in the clinical management of young children with first diagnosed UTI, US and renal scans performed at the time of acute illness were of limited value. VCUG was useful for identifying children with VUR if it could be proven that they benefit from prophylactic antimicrobial therapy. Renal scans performed 6 months later were useful in identifying children with scarring who might benefit from the performance of urine cultures in subsequent febrile illnesses.

Figure 4. N Engl J Med 2003; 348:195-202.

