**Table 8. Sample size for equivalence testing**

% of A and B with renal scarring on outcome DMSA scan	Sample size
0.10	79+190=269
0.13	100+238=338
0.15	112+269=380
0.20	141+337=477

- 1) Children in the CUTIE study who do not have VUR, and;
- 2) Children in the RIVUR study who do have VUR and are receiving placebo.

All comparisons assume  $\alpha=0.05$  (one-sided for equivalence – difference in proportions farther from zero in the same direction), power=80%, equivalence limit difference in proportions=0.10, expected difference in proportions=0 and ratio of numbers of children in A and B of 150:360 (150 in A and 360 in B) (Table 8). The rate of renal scarring is assumed to be equal in groups A and B, and is estimated in the 10-15% range—in the lower range of previous reports but more consistent with a population with first UTI drawn largely from primary care practices as opposed to subspecialty clinics. Based on

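### Severe scarring is to be tested for equivalence with the 10-point margin sized for any scarring; at low severe-scar rates a several-fold excess with VUR could be declared equivalent

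*Protocol*

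**What the plan says.** Protocol section 6.1.2 describes one test for Specific Aim 1. The difference in the proportion with any renal scar is calculated, and the analysts will "test whether the difference in proportions is less than 10% or not using a one-sided 0.05 significance level". Rejecting the null leads to the conclusion that the groups are equivalent. The same paragraph then adds a further comparison, labelled as secondary: "we will test using the same approach the proportion of children with severe scarring (grades 3 or 4 scarring on at least one kidney".

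Section 6.2 and Table 8 size that test with "power=80%, equivalence limit difference in proportions=0.10, expected difference in proportions=0", at an allocation of "150:360 (150 in A and 360 in B". The tabulated rates of any scarring run from 10% to 20%, and the rate "is estimated in the 10-15% range". Section 5.2 and Figure 7 (section 4.1) define severe scarring as grade 3 or 4 in at least one kidney, that is, more than 4 of 12 segments or global atrophy. The protocol gives no expected rate of severe scarring and no second margin.

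**The concern.** An absolute margin has meaning only against the event rate it is applied to. Ten points on a 15% rate of any scarring already tolerates a ratio of 1.67. Carried over to an outcome that occurs in perhaps 1-3% of children, the same ten points tolerates several times that rate. The study could then state that severe scarring is equivalent with and without VUR while its own data show a clear excess.

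This matters because severe scarring is the weightier outcome, and the protocol's background makes an excess plausible. Section 1.1.2 reports that kidneys with grade 3 or higher reflux showed large acute defects significantly more often than kidneys without reflux. An equivalence statement on severe scars would be read as support for the view that VUR does not mark the children at risk.

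**Working it through.** **Step 1. Reproduce Table 8.** With equal rates p, margin 0.10, one-sided 5% (z = 1.645), 80% power (z = 0.842) and 2.4 children without VUR for each child with VUR:

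n(VUR) = (1.645 + 0.842)² × p(1 − p) × (1 + 1/2.4) / 0.10²

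At p = 0.15 this is 6.18 × 0.1275 × 1.417 / 0.01 = 111.7, or 112 with VUR, and 2.4 × 111.7 = 268, or 269 without. Table 8 has 112+269. The other rows also agree with this one-sided formula (79+190, 100+238, 141+337). The margin is therefore an absolute 10 points, and it was sized only for any scarring.

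**Step 2. Compare the margin with the possible severe-scar rate.** Severe scarring cannot be more frequent than any scarring. If any scarring is 10%, the severe rate cannot exceed the margin. If any scarring is 15%, then 10/15, or two-thirds of all scars, would have to be severe for the rate to reach the margin.

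The ratio at which the true difference just meets the margin is (p + 0.10)/p, with p the rate without VUR:

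- Any scarring: 1.67 at 15% and 2.0 at 10%.
- Severe scarring: 3 at 5%, 4.3 at 3%, 6 at 2% and 11 at 1%.

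**Step 3. Chance of declaring equivalence.** Two years at 10% loss per year leaves 150 × 0.81 = 122 and 360 × 0.81 = 292. The severe-scar rates are assumptions. The probabilities are exact binomial sums over all outcomes in which the upper one-sided 95% limit for VUR minus non-VUR lies below 10 points. The protocol does not name the form of the limit, so three are shown. Farrington-Manning is the method behind the sample-size reference.

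| VUR v no VUR | Ratio | Agresti-Caffo | Wald | Farrington-Manning |
|---|---|---|---|---|
| 3% v 1% | 3 | 98% | 99% | 97% |
| 4% v 1% | 4 | 92% | 95% | 90% |
| 5% v 1% | 5 | 80% | 85% | 76% |
| 6% v 1% | 6 | 64% | 70% | 59% |
| 8% v 1% | 8 | 31% | 37% | 27% |
| 6% v 2% | 3 | 75% | 79% | 70% |
| 8% v 2% | 4 | 42% | 48% | 37% |
| 9% v 3% | 3 | 38% | 45% | 33% |

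In these unequal scenarios it makes no difference whether one limit or both are required to lie inside ±10 points.

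**Step 4. Observed data that would pass.** Take 11/150 (7.33%) v 4/360 (1.11%), a ratio of 6.6 with Fisher p = 0.0005. The difference is 6.22 points. The standard error is √(0.0733 × 0.9267/150 + 0.0111 × 0.9889/360) = 2.20 points. The upper Wald limit is 6.22 + 1.645 × 2.20 = 9.8 points, so the groups are equivalent under the rule. Agresti-Caffo and Farrington-Manning would just fail this table. At 10/150 v 4/360, a six-fold excess, all three pass.

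**Step 5. Could a smaller margin be used?** Take a severe rate of 2% in both groups and a 2-point margin: 6.18 × 0.0196 × 1.417 / 0.02² = 429, about 430 with VUR and 430 × 2.4 = 1,032 without. A 3-point margin at 3% needs 284+682. The study has 150+360.

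**The case against.** The best counter-argument is textual. The sentence just before the severe-scarring one uses the word approach for the reversal of null and alternative hypotheses. For recurrent UTI the protocol restates the 10% limit, but for severe scarring it does not. The margin might therefore be unspecified and left to an analysis plan that is not at hand. That reading is possible. But section 6.1.2 defines its test by the 10-point limit and the protocol offers no other, so a reader following the text would use it. The proposed change cures both readings.

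Several stronger statements are tempting, and the documents do not support them.

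- **The test can hardly fail, whatever VUR does.** It can. At 8% v 1% it passes about a third of the time, and at 8% v 2% less than half.
- **The protocol cites an 8- to 10-fold excess of severe scars.** The statement in section 1.1.2, "eight to ten times as likely as those with no VUR", concerns scarring in general, in some studies, and high-grade VUR only. The comparison group is all placebo children in RIVUR, grades I-IV. The finding on large acute defects is nearer, but it concerns acute lesions and counts a defect as large above 10% of the kidney, well short of grade 3. It makes an excess of severe scars plausible and does not measure one.
- **The earlier cohort gives the severe-scar rate.** Section 1.2.5 reports "renal scarring (mean ~8% of the renal parenchyma) noted in 26/272 (9.5%) children", at six months. A mean extent does not give the share above 4 of 12 segments. The subset argument in Step 2 does not need it.
- **A five-fold severe excess passes more easily than the primary test with no difference.** This holds only if the primary test must meet both limits, where 15% v 15% passes 66% of the time. The one-sided test that Table 8 sizes passes 79-82% (Agresti-Caffo to Wald), against 80-85% for 5% v 1%. The two are about the same.

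It is also fair that this analysis is labelled secondary, and that section 1.1.5 rests its inference about VCUG on the Aim 1 scarring rate, not on severe scars.

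**Conclusion.** The point holds in conditional form. The 10-point margin does not suit severe scarring, and at low severe-scar rates the rule as written would probably declare equivalence despite a several-fold excess in children with VUR. With 1% severe scarring in children without VUR, three- to six-fold excesses pass with about 64-99% probability (Agresti-Caffo to Wald). With 2%, a three-fold excess passes about 75-79% of the time. By 3%, a three-fold excess passes less than half the time.

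These figures rest on assumed severe-scar rates, on the 10-point reading of section 6.1.2, and on 10% loss per year. Section 3.1.1 gives 10% over the whole two years instead. That leaves 135 and 324 children and raises the chance slightly, to 80-87% at 5% v 1% (Farrington-Manning to Wald). The primary comparison of any scarring is not affected.

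**What to change.** In section 6.1.2, replace the instruction to test severe scarring in the same way as any scarring. State that severe scarring will be reported as the proportion in each group, with the risk difference and risk ratio and their 95% confidence intervals, and that no equivalence conclusion will be drawn from it.

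Setting a separate, smaller margin is not a workable alternative with the fixed sample. The change costs one sentence and no data. What is given up is a secondary equivalence claim that the design cannot support.

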### 6.1.3 Analysis Plans for Specific Aim 2 – Predictive Model

The primary approach to Aim 2 will be to use a multivariable logistic model-fitting approach. At the first step, all variables identified as predictors will be entered in univariate logistic regression models. Predictor variables that are associated with the outcome at the  $p < 0.2$  level will be considered as potential predictors/confounders and candidates for inclusion in the full multivariable models.

Multivariable modeling techniques will be used to develop prediction models for the development of renal scarring. Clinical judgment and strength of predictive variables in previous studies will force some variables to be included in the models regardless of their level of statistical significance (e.g., VUR grade, age, sex). Potential interaction variables to be considered in the models will be chosen based on the clinical judgment of the investigators and evidence from the literature, if both variables are candidates for inclusion in the model based on the first step.

The multivariable models will be developed using the best subset selection method. The best subset approach starts by fitting all single variable models and examining the log-likelihood of the model. Then all pairs of variables are entered into models and the log-likelihood calculated. The best two-variable models are those with the largest log-likelihood and a significant  $G^2$  statistic for the difference between the two-variable model and the two single-variable models nested in it. The  $G^2$  statistic is calculated as twice the difference in log likelihood between two nested models and has asymptotically a chi-square distribution with degrees of freedom equal to the difference in the number of parameters between the two nested models. The next step consists of examining all three-variable models and comparing those to the two-variable models. The process stops when the  $G^2$  statistic shows that adding variables no longer increases the log-likelihood significantly. The advantage of this process is that it is a comprehensive exploration of all available models, as opposed to the stepwise approach, which only explores the next best variable, and whose path may not lead to the best model. While this process is not feasible if there are too many variables to be explored, in this study, the number of variables is limited and this process therefore can be employed for optimal results. Finally, the process can lead to more than one optimal model (e.g. two or three models with somewhat different variables and comparable log-likelihoods). We will explore the content implications of different models and decide which model is best translated into a practical prediction rule for use in clinical practice. In the process of this modeling we will make sure that at any time an interaction variable is in the model, the two single variables forming the basis for the interaction are also included in the model.

Prediction model performance will be evaluated in terms of (1) discrimination (ability of the model to separate individuals with different outcomes); and (2) calibration, or fit (agreement between observed and expected probabilities). Discriminative ability will be measured using the c index, which is defined as the proportion of all pairs of subjects, one with and one without the outcome, in which the patient having the outcome had the higher predicted probability of having the outcome. The c index is equivalent to the area under an ROC curve, which is a reflection of the overall ability of the model to differentiate subjects with and without the outcome of interest. A c index of 0.5 indicates no predictive discrimination and a value of 1 indicates perfect separation of subjects with different outcomes. The discriminative performance of alternative versions of the model, generated by eliminating various predictors, will be compared. The most parsimonious model(s) that has nearly as much discriminant ability as the full model will be adopted. ROC curves for the final

candidate model(s) will be plotted by varying the positivity criterion for predicted risk in the smallest increments that the data support from 0% to 100% and plotting the corresponding sensitivities and specificities. For each predicted risk positivity criterion we will also calculate positive and negative predictive values and likelihood ratios.

The calibration of the logistic regression model will be tested by calculating Brier scores. The Brier score is the mean squared error of the probability predictions and ranges from 0 to 1. Zero indicates perfect calibration, one indicates complete mis-calibration, and up to 0.25 is considered chance agreement. For dichotomous events, the Brier score is given as  $n\sum(y_k - o_k)^2$ , where  $y_k$  is the predicted probability, and  $o_k$  is the observed outcome for each of the  $n$  forecast/event pairs. Calibration will also be measured using the Hosmer-Lemeshow goodness-of-fit statistic which uses chi-square tests after ordering observations by predicted probability, dividing them into equally sized groups and then calculating observed and expected probabilities in each group. Because the Hosmer-Lemeshow test is sensitive to the number of groups compared, we will perform the test on different numbers of equally sized groups.

We will use a bootstrap technique to evaluate the possibility that the proposed model(s) is overfit and thus not generalizable to other patient samples. The bootstrap repeatedly chooses a new data set at random (with replacement) from the original data set and recalculates new regression coefficients. The "bootstrapped variance" of the regression coefficients over all the data sets is used with the original regression coefficients to compute new bootstrapped p-values. Coefficients that lose statistical significance in the bootstrapped p-value are likely the result of overfitting. Compared with other validation techniques, such as split sampling and cross-validation, bootstrapping provides nearly unbiased estimates of predictive accuracy that are of relatively low variance, requires fewer model fits, and uses the entire data set for model development. If we find that the model is overfit, we will go back a step in the modeling process and redo the bootstrap on a one level simpler model.

Because the objective is to develop a practical prediction rules that clinicians can use in the clinical setting, we will develop a simple risk index using those predictors in the final model(s). To develop a risk index score for research purposes, one might use the regression coefficients for the individual risk factors as weights for calculating a score. However, a risk index that multiplies observed values by coefficients will not be practical. Therefore, we will explore the variables in the best model and assign each variable a transformed variable with values of 0, 1 or 0, 1, 2, where 0 indicates a normal or non-problematic range, and 1 indicates abnormal; or 1 and 2 moderate and severe problems. We will sum up the values and explore the risk score cutoff that best separates the children who develop renal scarring from those who do not. In recognizing the importance of not missing cases, a cutoff value may be chosen that is somewhat conservatively low. This will create false positives, but decrease the false negatives. Depending on the variables in the final model, we may explore both transformations of a variable to 0, 1 or 0, 1, 2 values. Further, although the multiple logistic regression modeling may give several competing models, the one that yields the more useful, simple discriminatory index will be the one chosen for implementation as a risk index. The risk index will be designed so that it approximates the predictive accuracy of the regression models from which it is derived. Using the same techniques discussed above, we will compare the discriminative ability and calibration of the regression model and its corresponding risk indices.

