## 2 STUDY OBJECTIVES

### 2.1 Specific Aims

Formatted: Bullets and Numbering

The Specific Aims of this study are:

- 1) To compare the proportion of children who develop renal scarring 2 years following a first or second episode of UTI among children in the proposed ancillary study who do not have VUR and children in the RIVUR study who do have VUR and are receiving placebo.

Hypothesis: The proportion of children who develop renal scarring among children in the ancillary study who do not have VUR and children in the RIVUR study who do have VUR and are receiving placebo will be equivalent (<10% absolute risk difference).

- 2) To develop a prediction rule that accurately identifies children at high risk of developing renal scarring as well as children with virtually no risk of developing renal scarring following a first or second episode of UTI.

Hypothesis: A prediction rule incorporating clinical and demographic factors associated with renal scarring will predict with >98% sensitivity and >50% specificity which children will develop renal scarring following a first or second episode of UTI. A prediction rule with these test properties would identify nearly all children who develop renal scarring while accurately assessing as low risk at least 50% of children who do not develop renal scarring.

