#### 6.1.4 Analyses for the Secondary Aims - Recurrence of UTI and Predictive Model

The definition of recurrent UTI as a secondary endpoint is that it has to meet the exact same stringent criteria as the index UTI and its onset occurs more than 2 weeks from the last day of treatment for the preceding UTI, or following a negative urine culture. The analytic approach of (1) testing for equivalence of proportion of recurrent UTIs between patients who had VUR and were treated with placebo after their first or second UTI (RIVUR patients) and patients who did not have VUR after their first or second UTI (recruited as patients to this study) and (2) building a predictive model will be identical to the approach described above for the renal scarring outcome.

In comparing differences in recurrent UTI between the two groups we will adjust for known risk factors for recurrent UTI (such as age, gender, race, circumcision status) using multivariable logistic regression models (for recurrent UTI (yes/no)) and Cox Proportional Hazards models (for the time to recurrent UTI). We will also determine whether the 2 groups are different in terms of other factors not known to be associated with recurrent UTI, and we will adjust for those factors as well in order to control for any potential unrecognized confounders.

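### The risk-index cutoff in 6.1.3 is not tied to the >98% sensitivity and >50% specificity by which Aim 2 is judged, so the operating point is left open until outcomes are seen

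*Protocol*

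**What the plan says.** Aim 2 (Protocol 2.1, repeated in the synopsis) gives a numerical success criterion: the rule "will predict with >98% sensitivity and >50% specificity which children will develop renal scarring following a first or second episode of UTI". Section 6.2 carries this into planning. It expects 66 scarred children among 510 and tabulates 95% confidence intervals at sensitivity 0.98 (N=66) and specificity 0.50 (N=444), among other values, in Table 10.

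Section 6.1.3 turns the final model into a simple index by summing items scored 0/1 or 0/1/2. For the cutoff of that index, the team will "explore the risk score cutoff that best separates the children who develop renal scarring from those who do not". It continues: "In recognizing the importance of not missing cases, a cutoff value may be chosen that is somewhat conservatively low". The accepted consequence is stated: "This will create false positives, but decrease the false negatives". No figure is attached to this lowering.

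For the regression model, 6.1.3 also plots sensitivity and specificity over all predicted-risk thresholds. Section 6.1.4 extends the plan to recurrent UTI, where "building a predictive model will be identical to the approach described above for the renal scarring outcome". Section 2.2 sets the same two targets for that outcome.

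**The concern.** Separating two groups as well as possible and reaching a sensitivity above 98% are different criteria, and they generally lead to different points on the ROC curve. The hypothesis needs the second. The text starts from the first and permits, without requiring, a move of unspecified size towards the second.

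Two things follow. The sensitivity and specificity reported for the final rule may sit at a point that the hypothesis does not concern. And whether Aim 2 succeeds can depend on how far the cutoff is lowered once the outcomes are visible. The aim also wants a group at almost no risk of scarring. A cutoff well short of 98% sensitivity would put an appreciable number of children who scar into that group.

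**Working it through.** **Inputs.** From Protocol 6.2: 510 children, 66 scarred (0.13 × 510 = 66.3), 444 unscarred. From 2.1: sensitivity >98%, specificity >50%. The protocol states no c index, so a range is used.

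**The plan's own figures.** Wilson score intervals reproduce Table 10 to rounding. Sensitivity: 53/66 gives 0.692–0.881, 59/66 gives 0.797–0.948, 65/66 gives 0.919–0.997. Specificity with N=444: 0.355–0.446, 0.454–0.546 and 0.554–0.645. Table 10 is sound.

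**What the target allows.** 65/66 = 98.5% passes and 64/66 = 97.0% fails. At most one scarred child may be missed.

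**What a best-separating cutoff would do.** Assume equal-variance normal scores and read best separation as the maximum Youden index. With d = √2 × z(c):
- sensitivity = specificity = Φ(d/2) at the Youden cutoff;
- specificity at 98% sensitivity = Φ(d − 2.054).

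| c | d | Youden sens. = spec. | Missed of 66 | Spec. at 98% sens. |
|---|---|---|---|---|
| 0.70 | 0.742 | 64.5% | 23.5 | 9% |
| 0.80 | 1.190 | 72.4% | 18.2 | 19% |
| 0.83 | 1.349 | 75.0% | 16.5 | 24% |
| 0.90 | 1.812 | 81.8% | 12.0 | 40% |
| 0.927 | 2.056 | 84.8% | 10.0 | 50% |
| 0.95 | 2.326 | 87.8% | 8.1 | 61% |

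The 98%/50% target needs d = 2.054 + 0, so c = Φ(2.054/√2) = 0.927. At that point the Youden cutoff misses 15%. With case-to-control SD ratios of 0.7 or 1.4, each set so that 98%/50% is just reached, it misses 14%.

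**How far the cutoff must move.** Going from the Youden point to 98% sensitivity takes specificity from 72% to 19% at c = 0.80, from 82% to 40% at 0.90, and from 85% to 50% at 0.927. That is more than a slight adjustment.

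**A coarse index.** Section 6.2 allows up to six covariates. Take six like 0/1 items, independent given outcome, with the prevalences and odds ratios of Table 9; those odds ratios are detectable values, not expected ones. Treat the prevalence as that in unscarred children. The item frequency in scarred children is q = o × OR/(1 + o × OR), where o = prevalence/(1 − prevalence). A scarred child scores 0 with probability m = (1 − q)⁶.
- Prevalence 0.30, OR 2.2: q = 0.485, m = 1.9%, expected 1.2 of 66.
- Prevalence 0.30, OR 2.8: q = 0.545, m = 0.9%, expected 0.6 of 66.
- Prevalence 0.20, OR 3.1: q = 0.437, m = 3.2%, expected 2.1 of 66.

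The chance of two or more misses, 1 − (1 − m)⁶⁶ − 66m(1 − m)⁶⁵, is 35%, 11.5% and 63% respectively. In those cases even a cutoff of 1 point fails the 98% requirement, and only labelling every child positive meets it. Where 1 point does pass, specificity is 0.7⁶ = 12% or 0.8⁶ = 26%.

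**The case against.** The strongest reply is that 6.1.3 does not commit to a Youden cutoff. It speaks of exploring, names no index, and leans explicitly towards fewer missed cases. This stands. A reader might infer that the rule as written misses about a quarter of scarred children; the documents do not support that. No c index or miss rate is stated. A quarter requires c of about 0.83, where specificity at 98% sensitivity is only 24%, so the hypothesis would fail at any cutoff and not because of how the cutoff was chosen.

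A reader might also infer that the plan cannot answer its own hypothesis. That is too strong. For the regression model, sensitivity and specificity are produced at every threshold, so specificity above 98% sensitivity can be read off, and Table 10 shows that the target was kept in view. For the index, 6.1.3 promises to compare discrimination and calibration by the same techniques, which may include the same sweep. A full sweep still does not say which cutoff is the rule under test.

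It can be said that a numerical cutoff algorithm belongs in the SAP, which is not shown. But the protocol does not stay silent here: it states a criterion, and that criterion differs from the one in the aim.

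Finally, choosing the cutoff to reach 98% in the development data meets half the hypothesis by construction, and on a coarse index it can end in calling every child positive. Both points are correct, and the fix has to deal with them.

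**Conclusion.** The point holds in a limited form. The cutoff criterion in 6.1.3 is not aligned with Aim 2 or Table 10, and the permitted lowering ("a cutoff value may be chosen that is somewhat conservatively low") is optional and has no number. The operating point at which the hypothesis is tested is therefore a choice made after outcomes are seen.

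The size depends on assumptions that the protocol does not make: a Youden reading and normally distributed scores. Under them the stated criterion misses between about 12% (c = 0.95) and just over 35% (c = 0.70) of scarred children. It misses about 10 of 66 at c of about 0.93, the lowest value at which 98%/50% is attainable with equal variances, against the one allowed. The mismatch is material at every c examined. What the team would actually report could be closer to the target, because the text allows a lower cutoff.

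**What to change.** In 6.1.3, replace the cutoff sentences with a rule along these lines: the cutoff is the highest index score at which sensitivity exceeds 98% (at most one missed case in 66), and specificity at that cutoff, with its 95% CI, is compared with 50%. If the only score meeting 98% is the one that labels every child positive, the hypothesis is reported as not supported.

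Add that sensitivity and specificity are reported with bootstrap optimism correction, repeating the cutoff choice in each resample. The bootstrap now described works on coefficient variances and p-values, so this extends its use. Give the best-separating cutoff as a descriptive second operating point only. Apply the same wording to the recurrent-UTI rule in 6.1.4.

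No new data or change in sample size is needed. The cost is a lower reported specificity: under the binormal assumption about 19% at c = 0.80 and 40% at c = 0.90, and possibly 0 on a coarse index. That is the quantity the hypothesis asks about.
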